4.2.2. Subjects with Impaired Hepatic Function

Subjects with mild, moderate, or severe hepatic impairment must also meet the following additional inclusion criteria to be eligible for participation in this study:

- 1) Aside from hepatic insufficiency, the subject must, in the opinion of the Investigator, be sufficiently healthy for study participation based upon medical history, physical examination, vital signs, and screening laboratory evaluations.
- 2) Must have diagnosis of chronic (> 6 months), stable hepatic impairment with no clinically significant changes within 3 months (90 days) prior to study drug administration (Day 1).
- 3) Must meet all of the following laboratory parameters at Screening:
 - ALT value $\leq 10 \times \text{ULN}$
 - AST value $\leq 10 \times \text{ULN}$

- Absolute neutrophil count $\geq 1,000/\text{mm}^3$
 - Platelets $\geq 25,000/\text{mm}^3$
 - Hemoglobin ≥ 9 g/dL
 - α -fetoprotein ≤ 50 ng/mL
- 4) Subjects with ***severe*** hepatic impairment must have a score on the Child-Pugh-Turcotte scale of 10-15 at Screening. If a subject's score changes during the course of the study, the score at Screening will be used for classification.
 - 5) Subjects with ***moderate*** hepatic impairment must have a score on the Child-Pugh-Turcotte scale of 7-9 at Screening. If a subject's score changes during the course of the study, the score at Screening will be used for classification.
 - 6) Subjects with ***mild*** hepatic impairment must have a score on the Child-Pugh-Turcotte scale of 5-6 at Screening. If a subject's score changes during the course of the study, the score at Screening will be used for classification.
 - 7) Subjects in Cohort 1: Non-smoking hepatic impairment subjects must have no use of tobacco, nicotine-containing, or THC-containing products within at least 14 days prior to study drug dosing, and cannot smoke or use these products during the study. Smoking hepatic impairment subjects must have smoked ≥ 10 cigarettes/day for at least 30 days and plan to continue smoking ≥ 10 cigarettes/day during the study.
 - 8) Subjects in adaptive Cohorts 2 and 3: Must be current non-smokers (no use of tobacco, nicotine-containing, or THC-containing products within the last 14 days prior to study drug dosing, and cannot smoke or use these products during the study).

4.2.3. Healthy Matched Controlled Subjects

Healthy matched control subjects must also meet the following additional inclusion criteria to be eligible for participation in this study:

- 1) Must, in the opinion of the Investigator, be in good health based upon medical history, physical examination, vital signs, and screening laboratory evaluations.
- 2) Must meet all of the following laboratory parameters at Screening:
 - INR $\leq 1 \times$ ULN
 - Albumin $\geq 1 \times$ LLN
 - Total bilirubin $\leq 1 \times$ ULN
 - AST value $\leq 1 \times$ ULN

- ALT value $\leq 1 \times$ ULN
- Alkaline phosphatase $\leq 1 \times$ ULN
- α -fetoprotein $\leq 1 \times$ ULN
- Negative Hepatitis B surface antigen (HBsAg)
- Negative Hepatitis B core (HBc) antibody
- Negative HCV antibody
- Screening laboratory evaluations (hematology, fasting lipids, chemistry, and urinalysis) must be within the normal range unless the results have been determined by the investigator to have no clinical significance.

4.3. Exclusion Criteria

4.3.1. All Subjects

Any subjects who meet *any* of the following exclusion criteria are not to be enrolled in this study.

- 1) Pregnant or lactating subjects
- 2) Have received any investigational compound within 30 days prior to study dosing
- 3) Concurrent participation in another therapeutic clinical trial
- 4) Current alcohol or substance abuse judged by the investigator to potentially interfere with subject compliance or subject safety
- 5) A positive test result for human immunodeficiency virus (HIV-1/HIV-2) antibody, hepatitis B (HBV) surface antigen or current HCV infection (exclude all subjects who test positive (reactive) for HCV antibody with repeat test HCV RNA detected)
- 6) Have poor venous access that limits phlebotomy
- 7) History of having donated blood within 56 days prior to check in (Day-1).
- 8) History of having donated plasma within 7 days prior to check in (Day -1).
- 9) History of prior allogeneic bone marrow progenitor cell or solid organ transplantation.
- 10) Currently registered on an organ transplantation list.
- 11) History of bleeding from esophageal varices within 90 days prior to check in (Day-1).

- 12) Have been treated with systemic steroids, immunosuppressant therapies, or chemotherapeutic agents within 3 months prior to Screening or expected to receive these agents during the study (eg., corticosteroids, immunoglobulins, and other immune- or cytokine-based therapies)
- 13) Significant serious skin disease, such as but not limited to rash, food allergy, eczema, psoriasis, or urticaria
- 14) Significant drug sensitivity or drug allergy (such as anaphylaxis or hepatotoxicity)
- 15) Known hypersensitivity to the study drugs, their metabolites (if applicable), or to formulation excipients (see Section 5.2.1)
- 16) Significant cardiac disease (including history of myocardial infarction based on ECG and/or clinical history, any history of ventricular tachycardia, congestive heart failure, or dilated cardiomyopathy with left ventricular ejection fraction <40%), a family history of Long QT Syndrome, or unexplained death in an otherwise healthy individual between the ages of 1 and 30 years.
- 17) Presence or history of cardiovascular disease, cardiomyopathy, and/or clinically significant cardiac conduction abnormalities.
- 18) Syncope, palpitations, or unexplained dizziness
- 19) Implanted defibrillator or pacemaker.
- 20) Severe peptic ulcer disease, gastroesophageal reflux disease, or other gastric acid hypersecretory conditions requiring prolonged (>6 months) medical treatment.
- 21) Medical or surgical treatment that permanently alters gastric absorption (eg, gastric or intestinal surgery). A history of cholecystectomy is not exclusionary.
- 22) Subjects with use of moderate or strong CYP3A or CYP2C9 inducers, or strong CYP2C9 inhibitors within 2 weeks prior to study drug administration will be excluded. Subjects with use of proton pump inhibitors within 1 week prior to study drug administration will be excluded. (Please see Section 5.6.1 for excluded Concomitant Medications)
- 23) Are unable to comply with study requirements or are otherwise believed, by the study investigator, to be inappropriate for study participation for any reason.

4.3.2. Subjects with Impaired Hepatic Function

Subjects with mild, moderate, or severe hepatic impairment meeting *any* of the following additional exclusion criteria are not to be enrolled in this study:

- 1) Aside from hepatic insufficiency, serious or active medical or psychiatric illness that, in the opinion of the Investigator, would interfere with subject treatment, assessment, or compliance with the protocol. This would include renal, cardiac, hematological, unstable hepatic, pulmonary (including chronic asthma), endocrine (eg, diabetes), central nervous, gastrointestinal (including an ulcer), vascular, metabolic (thyroid disorders, adrenal disease), immunodeficiency disorders, active infection, or malignancy that are clinically significant or requiring treatment.
- 2) Requires paracentesis > 1 time per month.
- 3) Subjects with hepatic impairment with co-morbid diseases requiring medication(s) must be taking the medication(s) without a clinically significant change in dose of con-meds for co-morbid diseases for > 3 months prior to screening.
- 4) Smoking Subjects in Cohort 1: Recent significant changes in smoking habits or the use of nicotine or nicotine containing products (ie, initiation, substantial increase or decrease or cessation of use) for at least 14 days prior to study drug dosing, or anticipated significant changes in smoking habits or the use of nicotine or nicotine containing products during the course of the study through the follow-up visit.
- 5) Positive test for drugs of abuse, including alcohol at Screening or on Day -1/check-in (Positive THC screen allowed for subjects in states/countries that have legalized THC containing substances)

All concomitant medications including over-the-counter and herbal products must be approved by the Investigator and Medical Monitor prior to study enrollment and study drug administration.

4.3.3. Healthy Matched Controlled Subjects

Healthy matched controlled subjects meeting *any* of the following additional exclusion criteria are not to be enrolled in this study:

- 1) Serious or active medical or psychiatric illness that, in the opinion of the Investigator, would interfere with subject treatment, assessment, or compliance with the protocol. This would include renal, cardiac, hematological, hepatic, pulmonary (including chronic asthma), endocrine (eg, diabetes), central nervous, gastrointestinal (including an ulcer), vascular, metabolic (thyroid disorders, adrenal disease), immunodeficiency disorders, active infection, or malignancy that are clinically significant or requiring treatment.
- 2) History of liver disease.

- 3) Have taken any prescription medications or over-the-counter medications, including herbal products, within 28 days prior to start of study drug dosing, with the exception of vitamins and/or acetaminophen and/or ibuprofen
- 4) Positive test for drugs of abuse, including alcohol at Screening or on Day -1/check-in
- 5) Subjects will be required to refrain from the use of nicotine, nicotine-containing products (including cigarette smoking) or THC-containing products for at least 14 days prior to first dose of study drug, and during the course of the study through the follow-up visit

5. STUDY DRUGS

5.1. Randomization and Blinding

This is an open-label, non-randomized study.

It is the responsibility of the Investigator to ensure that the subject is eligible for the study prior to enrollment. Subjects will be assigned a Screening number at the time of consent.

A minimum of 40 and a maximum of 80 male and non-pregnant, non-lactating female subjects with either impaired hepatic function of CPT classification A, B, or C or with normal hepatic function will be enrolled to 1 of the 3 cohorts as described in Section 6.1.

Study drug will be dispensed by the study pharmacist in an open-label fashion to the subjects.

All Screening and check-in (Day -1) tests and procedures must be completed prior to the administration of the first dose of study drug on Day 1. Once a subject number has been assigned to a subject, it will not be reassigned to another subject. If necessary, replacement subjects may be enrolled after discussion and approval from Sponsor. A new unique subject number will be assigned to the replacement subject.

A subject number schema will be provided to the study center by the Sponsor. Once eligibility is confirmed in consultation with the Sponsor, a subject number will be assigned by the Sponsor.

5.2. Description and Handling of Entospletinib

5.2.1. Formulation

Study drug entospletinib (ENTO, GS-9973) is available as 100 mg strength tablets. The tablets contain ENTO spray-dried dispersion (SDD) and commonly used excipients including mannitol, poloxamer 188, crospovidone, silicon dioxide, microcrystalline cellulose, magnesium stearate, polyethylene glycol, polyvinyl alcohol, talc, titanium dioxide, and FD&C blue #2 aluminum lake. ENTO SDD consists of ENTO, methanesulfonic acid, and hypromellose. The 100 mg ENTO tablets are blue, capsule-shaped, plain-faced, film-coated blue tablets.

5.2.2. Packaging and Labeling

ENTO 100 mg tablets are packaged in white, high density polyethylene (HDPE) bottles. Each bottle contains 60 tablets, silica gel desiccant and polyester packing material. Each bottle is enclosed with a white, continuous thread, child-resistant polypropylene screw cap with an induction-sealed and aluminum-faced liner.

Study drug(s) to be distributed to centers in the US and other participating countries shall be labeled to meet applicable requirements of the United States Food and Drug Administration (FDA), EU Guideline to Good Manufacturing Practice - Annex 13 (Investigational Medicinal Products), and/or other local regulations.

5.2.3. Storage and Handling

ENTO should be stored at a controlled room temperature of 25°C (77°F); excursions are permitted from 15°C to 30°C (59°F to 86°F). Storage conditions are specified on the label. Until dispensed to the subjects, all bottles of study drugs should be stored in a securely locked area, accessible only to authorized site personnel.

To ensure the stability and proper identification, study drugs should not be stored in a container other than the container in which they were supplied. Keep the bottle tightly closed to protect from moisture. Consideration should be given to handling, preparation, and disposal through measures that minimize drug contact with the body. Appropriate precautions should be followed to avoid direct eye contact or exposure through inhalation when handling.

5.3. Dosage and Administration of Study Drug

Following completion of Screening and Day -1 assessments, eligible subjects will be enrolled in 1 of 3 cohorts and receive multiple doses of 100 mg twice a day (BID) ENTO (1 x 100 mg tablet) starting on Day 1 in the fasted state.

When feasible, dosing in a control subject with normal hepatic function will occur after the matched subject with impaired hepatic function has completed the PK assessments, except for control subjects that were already matched to a subject with impaired hepatic function in a previous cohort, as permitted in adaptive Cohorts 2 and 3.

Subjects in adaptive Cohort 2 (Severe Hepatic Impairment) and/or adaptive Cohort 3 (Mild Hepatic Impairment) will be enrolled as determined by safety and/or PK data non-smoking subjects and healthy, matching controls in Cohort 1 (Moderate Hepatic Impairment). Specifically, Cohort 2 will be initiated if supported by safety and PK **findings from non-smoking hepatic impairment subjects and matching, healthy control subjects in Cohort 1**. Cohort 3 will be enrolled if a clinically meaningful change (≥ 2 -fold mean difference from matched healthy controls) in the exposures of ENTO and/or metabolite (if applicable) exposure is identified in non-smoking hepatic impairment subjects in Cohort 1.

5.4. Fasting and Meals

All study treatments will be administered at approximately the same time each day with 240 mL of water following an overnight fast (no food or drinks except water, for at least 8 hours).

When ENTO is administered twice a day, the evening dose of ENTO will be administered approximately 12 hours after the AM dose. Subjects should continue fasting for 2 hours post AM dose and 2 hours before and 2 hours after the PM dose. Only the AM dose of ENTO will be given on Day 5.

On the days of intensive pharmacokinetic sampling, study treatments will be administered in the morning following an overnight fast (no food or drinks except water, for at least 8 hours). Subjects will continue to fast until after collection of the 4-hour pharmacokinetic samples,

relative to study drug dosing. Additionally, subjects will be restricted from water consumption 1 hour before until 2 hours after dosing, except for the 240 mL given with the study treatment.

All meals and/or snacks given to subjects during their stay in the clinical study facility will be standardized for all subjects and should be similar in calorie and fat content and taken at approximately the same time each day. All meals provided must be approved by the Sponsor. Components of meals (eg, margarine, jelly, bread) should be given to subjects in individual portions (eg, 1 tablespoon) per the approved meal schedule. The provision of meal components in bulk (eg, a jar of jelly for subjects to share) should not be practiced. All meals should be given at approximately the same time each day (eg, 07:30, 12:00, and 18:00).

5.5. Dispensing, Accountability, and Disposal or Return of Study Drug

The Investigator (or designee, eg, study center pharmacist) will acknowledge receipt of the study drug (after reviewing the shipment's content and condition) from Gilead (or designee). The Investigator will maintain an accurate inventory of all study drug(s). Each dose of the study drug(s) administered at the study center will be administered by qualified study center staff. The dose of study drug(s) administered to subjects in the clinic under the supervision of staff will be accurately recorded on the Study Drug Accountability Form provided by Gilead (or on equivalent documentation maintained by the study center), which indicates the date and quantity of each dosage formulation dispensed to individual subjects.

Gilead recommends that used and unused study drug supplies, including empty containers, be returned to the shipping facility from which it came or Gilead Sciences for destruction following drug accountability and drug inventory reconciliation.

If returning drug supplies to the shipping facility from which it came or to Gilead Sciences is not possible, the monitor will evaluate the site's SOP for study drug disposal/destruction in order to ensure that it complies with Gilead's requirements. At the end of the study, following final drug inventory reconciliation by the monitor, the study site will dispose of and/or destroy all unused study drug supplies, including empty containers, according to these procedures.

5.6. Concomitant Medications and Other Protocol Restrictions

5.6.1. Concomitant Medications

The following medications are excluded while subjects are participating in the study:

For subjects with normal hepatic function:

- Any prescription medications and over-the-counter medications including herbal products and antacids with the exception of vitamins, and/or acetaminophen and/or ibuprofen. However, the short term use of topical hydrocortisone cream or A&D ointment to treat minor skin irritation due to ECG leads will be allowed. If a subject requires use of a disallowed medication, a request for such use must be reviewed by the Sponsor and if approved, subjects may continue to participate in the study.

For all subjects:

- Any and all illegal or illicit drug use, including use of prescription drugs outside the care of the prescribing physician.
- Subjects may not be taking rifaximin within 7 days prior to baseline (Day -1) or during the study. Rifaximin is a substrate of P-gp, OATP1B1 and OATP1B3; in a clinical DDI study with cyclosporine (an inhibitor of these transporters), a 124-fold increase in rifaximin exposure was observed. ENTO is an inhibitor of P-gp, OATP1B1 and OATP1B3 and a similar DDI with rifaximin may occur. Rifaximin exposures are also significantly increased in subjects with mild, moderate and severe hepatic impairment. Further, rifaximin activates PXR at higher exposures leading to induction of drug metabolizing enzymes, therefore the use of rifaximin in this study may significantly confound the evaluation of the effect of hepatic impairment on ENTO PK.

Subjects with hepatic impairment:

- Subjects with hepatic impairment with co-morbid diseases requiring medication(s) must be taking the medication(s) without a clinically significant change in dose for > 3 months prior to screening.
- The use of moderate or strong CYP3A or CYP2C9 inducers, or strong CYP2C9 inhibitors within 2 weeks prior to study drug administration and during the study is prohibited. The use of proton pump inhibitors within 1 week prior to study drug administration and during the study is prohibited.
- All concomitant medications must be approved by the medical monitor (or the clinical pharmacologist) prior to enrollment.

5.6.2. Other Protocol Restrictions

- Subjects will be required to refrain from the consumption of food and beverages containing alcohol products 72 hours prior to the first dose of study drug and during the course of the study through the follow-up visit.
- Subjects will be required to refrain from the use of nicotine or nicotine-containing products and THC-containing products for at least 14 days prior to first dose of study drug, and during the course of the study through the follow-up visit. This restriction does not apply to smoking hepatic impairment subjects enrolled in Cohort 1.
- Subjects will be required to refrain from consumption of grapefruit juice, grapefruits, and Seville orange juice 72 hours prior to the first dose of study drug and during the course of the study through the follow-up visit.
- While confined at the study center, tea, coffee, chocolate, and other foods and beverages containing caffeine and other methyl xanthines will be prohibited on each dosing day. At all other times, caffeine-containing beverages and foodstuffs may be served or withheld in accordance with normal study center practice. Caffeine-containing beverages and foodstuffs will not be restricted while subjects are outside of the clinic.

- Subjects will be encouraged to avoid strenuous or prolonged exercise, as well as saunas, steambaths, and sunbathing or other prolonged UV exposure, eg, in a tanning salon, from the Screening evaluation until completion of the follow-up visit, as these activities are known to affect certain clinical laboratory test parameters, (eg, creatine kinase (CPK)) and will provide false indicators of a potentially treatment-related toxicity.

Upon every admission to the clinic, each subject will be questioned as to their compliance with the above protocol restrictions. If a subject is unable to comply with any of the restrictions described above, the subject's continued participation in the study will be reevaluated by the Investigator in consultation with the Sponsor.

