In vitro studies indicate that ENTO is primarily metabolized by CYP2C9, and to a lesser extent by CYP3A and CYP1A2. Use of nicotine-containing or THC-containing products may induce CYP1A2, which has the potential to affect ENTO metabolism. Due to lower observed ENTO exposure in smokers in Cohort 1, enrollment in Cohort 1 has been expanded to enroll 10 smokers with moderate hepatic impairment (for 8 evaluable) and appropriate matched healthy controls, in order to further investigate the impact of smoking on ENTO PK. To avoid the potentially confounding effect of smoking on the assessment of hepatic impairment on ENTO PK, additional non-smoking subjects with moderate hepatic impairment will also be enrolled in Cohort 1 (10 enrolled for 8 evaluable, and appropriate healthy, matched controls). In Cohorts 2 and 3, only non-smoking subjects with hepatic impairment will be enrolled so that an accurate assessment of the effect of hepatic impairment on ENTO PK can be made, without the potentially confounding effect of smoking.

The trial will enroll subjects with chronically impaired hepatic function and healthy controls, matched for body mass index, age, and sex. This study will proceed in a staggered fashion. Dosing of subjects with mild and/or severe hepatic impairment will occur only after the review of safety and PK from smoking and non-smoking subjects with moderate hepatic impairment. Specifically, Cohort 2 will be initiated if supported by safety and PK findings from subjects in Cohort 1. Cohort 3 will be enrolled if a clinically meaningful change (≥ 2 -fold mean difference from matched healthy controls) in the exposures of ENTO and/or metabolite (if applicable) exposure is identified in non-smoking hepatic impairment subjects in Cohort 1.

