### 5.2.2. Statistical Comparative Analysis

To evaluate the PK effect of hepatic impairment on ENTO and/or its metabolites (if applicable), the PK parameters ( $AUC_{0-12}$  (day 1),  $AUC_{tau}$  (day 5), and  $C_{max}$  (day 1 and 5)), will be compared between impaired hepatic function group (test) vs normal hepatic function group (reference)

within each smoking status group (Cohort 1 only) after natural log transformation. The primary comparison will be based on day 5 PK parameters ( $AUC_{\tau}$  and  $C_{\max}$ ).

To evaluate the smoking effect on PK of ENTO and/or its metabolites (if applicable), the PK parameters ( $AUC_{0-12}$  (day 1),  $AUC_{\tau}$  (day 5), and  $C_{\max}$  (day 1 and 5)), will be compared between smoking group (test) vs nonsmoking group (reference) within Cohort 1 hepatic impaired subjects after natural log transformation. The primary comparison will be based on day 5 PK parameters ( $AUC_{\tau}$  and  $C_{\max}$ ).

A parametric (normal theory) ANOVA model will be fitted to the natural log-transformed PK parameter using SAS® PROC MIXED. The model will include hepatic function as a fixed effect. The 2-sided 90% CIs will be constructed for the ratio of geometric least-squares means (impaired hepatic function group /normal hepatic function group).

The following SAS® PROC MIXED code will be used in the comparison analysis described above and the 90% confidence intervals (CIs) will be constructed for the ratio of geometric least-squares means of PK parameters.

```
Proc Mixed method=reml;
*where smoking status eq "Yes"; Cohort 1 only
*where smoking status eq "No"; Cohort 1 only
*where hepatic impaired, Cohort 1 only
  class hepgrp;
  *class smoking status;
  model lnest = hepgrp / ddfm=kr;
  repeated / group = hepgrp;
  lsmeans hepgrp / e diff cl alpha = 0.1;
  estimate 'Impaired versus Normal' hepgrp 1 -1 / cl alpha = 0.10;
  *model lnest = smoking status / ddfm=kr;
  *repeated / group = smoking status;
  *lsmeans smoking_status / e diff cl alpha = 0.1;
  *estimate 'Smoking vs Nonsmoking HI subjects in Cohort 1' smoking_status 1 -1 / cl
alpha = 0.10;
  ods output Estimates = LS_Diffs LSMeans = LS_Means CovParms = MSE;
Run;
```

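### Section 5.6.2 lifts the THC restriction along with the nicotine restriction for Cohort 1 smokers, so where THC is legal the smoking contrast may not reflect cigarettes alone

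*Protocol*

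**What the plan says.** **The restriction and the exemption.** Protocol 5.6.2 puts nicotine and THC in one bullet: "Subjects will be required to refrain from the use of nicotine or nicotine-containing products and THC-containing products for at least 14 days" before the first dose and through follow-up. It then states: "This restriction does not apply to smoking hepatic impairment subjects enrolled in Cohort 1". The exemption does not separate the two substances.

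**The groups compared.** Protocol 4.2.2 item 7 says "Non-smoking hepatic impairment subjects must have no use of tobacco, nicotine-containing, or THC-containing products within at least 14 days prior to study drug dosing", and bars these products during the study. The same item defines Cohort 1 smokers by cigarettes only (at least 10 a day) and is silent on THC for them. Protocol 4.3.2 item 4, the stability rule for smokers, covers smoking habits and nicotine. Protocol 4.3.3 item 5 requires healthy controls to be free of both nicotine and THC.

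**Rules that still bind smokers.** Protocol 4.3.2 item 5 excludes any impaired subject with a positive drug screen at Screening or Day -1, with one exception: "Positive THC screen allowed for subjects in states/countries that have legalized THC containing substances". Protocol 5.6.1 bars illegal or illicit drug use for all subjects.

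**Why THC matters here.** Protocol 1.3: "Use of nicotine-containing or THC-containing products may induce CYP1A2, which has the potential to affect ENTO metabolism". The same section says that "ENTO is primarily metabolized by CYP2C9, and to a lesser extent by CYP3A and CYP1A2".

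**The analysis.** Under SAP 5.2.2, Day 1 and Day 5 parameters "will be compared between smoking group (test) vs nonsmoking group (reference) within Cohort 1 hepatic impaired subjects". Smoking status is the only term in that model.

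**The concern.** A secondary objective is the effect of smoking on ENTO PK in moderate impairment. Protocol 1.3 says that Cohort 1 was expanded because lower exposure had been seen in smokers. For that contrast to describe cigarettes, the two groups should follow the same rule on other suspected CYP1A2 inducers. They do not: THC use breaches the protocol for a non-smoking impaired subject but is permitted for a Cohort 1 smoker where THC is legal.

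If THC does induce CYP1A2, its use among smokers would lower exposure in the same direction as the signal under study, and the analysis would count it as a smoking effect. The smoker-stratum impaired/normal ratio has the same asymmetry, because its controls must be THC-free.

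**Working it through.** **Step 1: who may use THC, by group and place.**

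| Group | THC legalized | THC not legalized |
|---|---|---|
| Cohort 1 impaired smokers | Permitted (5.6.2 exemption); positive screen accepted (4.3.2 item 5) | Positive screen excludes (4.3.2 item 5); illicit use barred (5.6.1) |
| Cohort 1 impaired non-smokers | Barred (4.2.2 item 7, 5.6.2), but a positive screen does not by itself exclude (4.3.2 item 5) | Barred; positive screen excludes |
| Healthy controls | Barred (4.3.3 item 5); positive screen excludes (4.3.3 item 4) | Barred; positive screen excludes |

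The rule is asymmetric only in the first column.

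**Step 2: could the planned data or model separate THC from cigarettes?** The model has no THC term and no THC sensitivity analysis is planned. The history in Protocol 6.9.2 names nicotine, alcohol and illegal drugs, so legal THC use may go unrecorded. Urine drug screens are scheduled at Screening, Day -1, Day 5, Day 9 and follow-up. The wording of 4.3.2 item 5 implies that they detect THC.

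**Step 3: size, for illustration.** The plan states no figure for this bias, so there is none to reproduce.

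- From the documents: 8 evaluable subjects per group; log-scale SD 0.455 (Protocol 8.7).
- Assumed: k of 8 smokers use THC, with k = 2 or 4. THC multiplies a user's AUC by f = 0.6, 0.7 or 0.8 beyond any cigarette effect. For the probabilities, the true cigarette effect is nil. The documents give neither THC prevalence nor an effect size.

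The expected smoker/non-smoker geometric mean ratio is multiplied by f^(k/8); for example, 0.6^(4/8) = 0.775 and 0.8^(2/8) = 0.946.

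The probability that the upper 90% limit is below 1 was simulated with k users and 8 − k non-users in the smoking group. A separate variance was estimated per group, as in the SAP model, with Satterthwaite degrees of freedom standing in for Kenward-Roger.

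| k of 8 | f | Ratio multiplied by | P(90% CI below 1) |
|---|---|---|---|
| 0 | – | 1.00 | 0.05 |
| 2 | 0.8 | 0.946 | 0.07–0.08 |
| 2 | 0.7 | 0.915 | 0.09 |
| 2 | 0.6 | 0.880 | 0.11 |
| 4 | 0.8 | 0.894 | 0.11 |
| 4 | 0.7 | 0.837 | 0.16 |
| 4 | 0.6 | 0.775 | 0.23 |

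Treating the effect as a uniform shift with the SD held at 0.455 would give 0.12 to 0.28 for k = 4. That overstates it, because mixing users and non-users widens the spread: for k = 4 and f = 0.6, the SD is about √(0.455² + 0.25 × (ln 0.6)²) = 0.52.

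**Step 4: scale against precision.** SE = 0.455 × √(2/8) = 0.2275, and t(0.95, 14 df) = 1.761. The 90% CI therefore runs from the estimate divided by exp(1.761 × 0.2275) = 1.49 to the estimate times 1.49. Shifts of 5–11% (f = 0.8) lie well inside that width; the shift of 22.5% (k = 4, f = 0.6) is also within it, but is not negligible.

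**The case against.** The strongest reply is that the gap is narrow. A reader might infer from 5.6.2 that nothing limits THC in Cohort 1 smokers. The documents do not support that: 4.3.2 item 5 excludes a positive screen except where THC is legalized, and 5.6.1 bars illicit use for everyone. This stands, and it confines the problem in effect to legalized places. It does not remove it, because the screen exception shows that THC-positive impaired subjects are expected.

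A reader might also infer that any difference between smokers and non-smokers could not be due to cigarettes, or that the bias must lower exposure in smokers. Neither follows. There is bias only if THC users are enrolled, and Protocol 1.3 says only that THC may induce CYP1A2, a lesser pathway than CYP2C9. Use by non-smokers in breach of the rule would pull the other way.

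The assumed effects may be generous, since what matters is THC's addition in people already smoking at least 10 cigarettes a day. A CI lying below 1 is also only a yardstick: the SAP sets its criterion (upper bound below 2.0) for the hepatic comparison and none for smoking. Both points stand.

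The consequence is limited too. Smoking is a secondary objective, and Protocol 3.1 and 5.3 base the Cohort 2 and 3 decisions on non-smokers and their controls. The smoker-stratum impaired/normal ratio already contains the whole cigarette effect because controls must be nicotine-free; THC only adds to that.

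**Conclusion.** The asymmetry is real. The protocol treats THC as a possible inducer, keeps it out of both comparison groups by rule, and lifts that rule for Cohort 1 smokers. Where THC is legal and users are enrolled, the smoking contrast could not be attributed to cigarettes alone, and the planned analysis would not show how far THC contributed.

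The size cannot be derived from the documents. Under the assumptions above, the ratio is multiplied by about 0.77 to 0.95, and the chance of a CI below 1 rises from 5% to between about 7–8% and 23%. With no THC users among the smokers, there is no such bias. The documents support neither a general permission for THC nor a certain bias. Priority is low to moderate: the point bears mainly on a secondary objective, but the check is cheap.

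**What to change.** 1. **SAP 5.2.2.** Repeat the Day 5 smoking contrast and the smoker-stratum impaired/normal ratio (AUCtau and Cmax) without Cohort 1 impaired subjects whose Day -1 or Day 5 urine screen is THC-positive. Report both results side by side, with the number removed from each group. The screens are already scheduled, so the cost is one sensitivity analysis. The downside is that a group may fall below 8 and the interval widen, so the result is descriptive. This step stands alone, and it is the only one that helps with smokers already enrolled.

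2. **Protocol, for any further enrolment.** Reconcile 5.6.2, 4.2.2 item 7, 4.3.2 item 5 and 5.6.1 so that the THC rule for Cohort 1 smokers is consistent with the rule for the groups they are compared with. Rewording 5.6.2 alone would leave the screen exception in 4.3.2 item 5 in place. The cost is a short wording change and possibly a smaller pool of eligible smokers.
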